3. STUDY DESIGN

The Application of Economics & Social psychology to improve Opioid Prescribing Safety (AESOPS) pilot study involves 41 Northwestern Medicine clinicians for which the primary aim is to test the feasibility of three interventions based on behavioral economic principles to reduce the reliance on opioids and encourage safe and effective pain management. The study period includes a 34 week baseline period and 34 week study intervention period. The primary outcome is average weekly morphine milligram equivalents (MME) prescribed per-clinician.

4. SELECTION AND ENROLLMENT OF PARTICIPANTS

4.1 Inclusion Criteria

The subjects involved in this trial are clinicians from one clinical site in Illinois. Clinicians must meet the following inclusion criteria to participate in this study: 1) treat adult patients and 2) practice at one of the study clinics.

An office visit is eligible for inclusion in the outcome denominator if: 1) the patient was 18 years old or older, 2) the provider and practice site were enrolled in the study, and 3) the visit occurred during the 6-month intervention period.

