9.1 General Design Issues

Hypotheses

Our primary hypothesis is that clinicians receiving behavioral economic interventions will have lower opioid prescribing rates post-intervention as compared to baseline. We will estimate weekly milligram morphine equivalent for each clinician and observe the change each month. This will capture CDC guideline prescribing endpoints.

Design

The Application of Economics & Social psychology to improve Opioid Prescribing Safety (AESOPS) R21 is a pilot study to test the feasibility of clinical decision support nudges within the electronic health record to discourage unnecessary opioid prescribing through the application of "behavioral insights"— empirically-tested social and psychological interventions that affect choice. Over a 34 week study period, participating clinicians will receive any of three nudges when eligibility criteria are met within a patient's chart: 1) **Opioid naïve**: Visit where the order is for an included opioid and there is no prior opioid prescription with a start date of greater than 1 day and less than 91 days, 2) **At-risk for long term use**: Visit where the order is for an included opioid there is a prior opioid prescription with a start date greater than 1 day and less than 91 days, and there is no prior opioid prescription with a start date greater than 90 days, and 3) **Long-term opioid recipient**: Total opioid doses are at least 50 MME per day, there are two or more prior opioid prescriptions with two different start dates both greater than 1 day and less than 91 days, and there is a prior opioid prescription with a start date greater than 90 days and less than 181 days.

Outcome Measures

The primary outcome is change in weekly milligram morphine equivalent from baseline to post intervention period. We will estimate weekly milligram morphine equivalent for each clinician and observe the change each month. This will capture CDC guideline prescribing endpoints.

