9.5 Data Analyses

For sample descriptive statistics, we will use means and medians for continuous measures, frequencies for count data, and standard deviations and interquartile ranges for variance. For inferential analysis, our primary hypothesis is that milligram morphine equivalent dose will decrease for persons on high doses of opioid therapy.

10. Statistical Analysis

Measures

The primary outcome is average weekly morphine milligram equivalents (MME) prescribed per-clinician. We assessed change in average per-clinician weekly MME from the 34-week baseline period before, to the 34-week period post-intervention using a mixed-effects, knotted spline, left censored regression to account for baseline differences in prescribing, a non-linear change in the rate of opioid prescribing from baseline to post-intervention, and an inflated number of weeks with an average MME of zero, respectively. Predictors include the fixed effects time in weeks, time with a knot at the intervention start, and a random intercept for clinician. The density function to achieve maximum likelihood estimates for a left censored regression is the observed probability of y_i assuming normal distribution ($x_i\beta, \sigma^2$) given that $y_i > 0$, weighted by the probability that y_i is above a censoring threshold, in this case zero.² Because uncensored observations are often skewed, we used log average weekly MME as our dependent variable. The percentage change in log MME per one unit increase in the uncensored, or latent variable was

measured using:

$$\log(MME)^* = \beta_0 + \beta_1 Time + \beta_2 (Time - t^*) + \zeta + error^1$$

where $\log(MME)^*$ is the latent, uncensored variable, time is the number of weeks, t^* is the spline knot for the intervention start, and ζ is the clinician random effect.¹ We adjusted the coefficients by calculating the average partial effect to interpret not just the linear change in $\log(MME^*)$, but the non-linear likelihood that $\log(MME^*)$ is uncensored, resulting in comparable estimates to ordinary least squares.²

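### Section 4.1 defines a visit denominator that is never linked to weekly MME per clinician, so a progressive fall in visits, or clinician departures, can mimic an intervention effect

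*Combined protocol and SAP*

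**What the plan says.** All references are to the combined protocol and SAP.

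- **Hypothesis (section 9.1).** The expectation is that "clinicians receiving behavioral economic interventions will have lower opioid prescribing rates post-intervention as compared to baseline". The denominator of the rate is not stated.
- **Visit denominator (section 4.1).** "An office visit is eligible for inclusion in the outcome denominator if: 1) the patient was 18 years old or older", the provider and site are enrolled, and "3) the visit occurred during the 6-month intervention period".
- **Outcome.** Section 10: "The primary outcome is average weekly morphine milligram equivalents (MME) prescribed per-clinician". The Précis and sections 1.1 and 3 say the same. Section 9.1 words it as a change: "The primary outcome is change in weekly milligram morphine equivalent from baseline to post intervention period", and adds "We will estimate weekly milligram morphine equivalent for each clinician and observe the change each month". Section 9.4.1 is similar. None of these divides by visits.
- **Model (section 10).** A left-censored mixed regression on log MME. "Predictors include the fixed effects time in weeks, time with a knot at the intervention start, and a random intercept for clinician". The censoring is motivated by "an inflated number of weeks with an average MME of zero".
- **Design.** There are 41 clinicians, with a 34-week baseline and a 34-week intervention period (section 3). There is one clinic and no randomization (sections 6.2.2 and 9.2), and no secondary outcomes (section 9.4.2).

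The documents do not mention an offset, a visit-count covariate, clinician leave or departure, or weeks without visits.

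**The concern.** Weekly MME is the product of visits and MME per visit. The intervention is meant to act on the second factor, and the outcome as most sections word it responds to both. The clinician random intercept absorbs stable differences in volume between clinicians, but not changes in volume over time.

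With no concurrent control, the before-after contrast is the only evidence on the sole primary outcome. Two adjoining 34-week periods cannot cover the same calendar months, so leave and clinic volume could plausibly differ between them. A clinician who is away, or has left, produces zero MME. Section 10 as written would treat that week in the same way as one in which eligible patients were seen and no opioid was ordered.

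The denominator rule does not help as it stands. Read literally it excludes every baseline visit, and its 6-month window does not match the 34-week intervention period.

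**Working it through.** The plan gives no sample size, power or effect size for this outcome, so there is no figure to reproduce. The check has three parts.

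**1. Time windows.** Six months is 6 × 365.25 / 12 / 7 = 26.1 weeks, and 34 weeks is 7.8 months. The section 4.1 window therefore matches neither the intervention period in section 3 nor the baseline.

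**2. Identity.** Weekly MME = visits × MME per visit. Hold MME per visit constant and let a clinician be absent for k of the 34 intervention weeks, with full attendance at baseline. The change in mean weekly MME is −k/34:

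| Weeks absent | Change in mean |
|---|---|
| 1 | −2.9% |
| 2 | −5.9% |
| 4 | −11.8% |
| 7 | −20.6% |

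**3. Simulation with no true change in prescribing per visit.**

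*Inputs from the plan:* 41 clinicians, 34 + 34 weeks (41 × 68 = 2,788 clinician-weeks), left-censoring at zero, a clinician random intercept, time, and post-knot time taken as zero before the knot.

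*Assumed inputs:* about 40 visits a week, an opioid order at about 4% of visits, 8% of weeks absent, lognormal MME per order, and a log(1 + MME) scale because section 10 does not say how zeros are logged. There were 40 runs per scenario.

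The entries are the mean slope-change coefficient per 34 weeks and, in brackets, the share of runs significantly negative.

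| Scenario | Weekly total, all weeks kept | MME per visit, zero-visit weeks dropped |
|---|---|---|
| No change | 0.07 (0.00) | 0.03 (0.00) |
| Visits ramp down 20% | −0.74 (0.33) | −0.21 (0.10) |
| Visits ramp down 40% | −1.65 (0.95) | −0.52 (0.55) |
| 5 of 41 clinicians leave in week 45 | −1.14 (0.53) | 0.02 (0.05) |
| One-time 20% step down in visits | 0.20 (0.03) | 0.04 (0.03) |
| Absence steps from 8% to 20% | 0.03 (0.00) | 0.06 (0.00) |

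With 40 runs the standard error of a share is at most about 0.08, for example √(0.53 × 0.47 / 40) = 0.079.

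*Why a step does not register.* The knot sits at the midpoint of the 68 weeks. A step there is antisymmetric about the knot, so the straight-line time term absorbs it. The slope-change term responds to what is symmetric about the knot. The raw mean still falls: by 20% for the visit step, and by 1 − 0.80/0.92 = 13.0% for the absence step.

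*Which adjustment works.* The per-visit ratio removed the departure artefact but only part of the volume artefact, because the share of zero weeks still depends on the number of visits. Adding log visits was examined under other assumptions: 20 visits a week, orders at 15% of visits, 8% absence, and no clinician intercept in the fit. The figures are the post-knot average partial effect at week 34, over 40 runs.

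| Scenario | Weekly total, all weeks kept | Zero-visit weeks dropped, log visits added |
|---|---|---|
| No drift | −0.09 | −0.04 |
| Absence drifts from 8% to 18% | −0.71 | −0.04 |
| Visits fall 20% | −0.46 | 0.00 |

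A repeat on these inputs with 25 runs gave −0.57 for a gradual 20% fall in visits and +0.08 (SE 0.07) for a step, so the −0.46 is best read as belonging to a gradual fall. In the same repeat the per-visit ratio left −0.17 under the gradual fall.

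**The case against.** **Average may already mean per visit.** A single clinician-week has an average only if something within it is averaged, and the eligible visit is a candidate. Weeks without visits would then be undefined and drop out. This stands as an ambiguity. A reader might infer that the outcome is certainly an undivided total, but the documents do not establish that. Most sections read as a total, and none says per visit.

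**Not every volume change biases the intervention term.** A reader might infer that any shift in attendance passes straight into it, so that the study cannot tell safer prescribing from less clinic time. The model has a slope change and no step term, and the step scenarios left that term near zero. The vulnerability is to progressive decline and departures, and separately to a step in the raw baseline-to-post change that section 9.1 names as the outcome.

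**Baseline visits can be counted.** A reader might infer from section 4.1 that no baseline denominator can exist. Sections 6.1 and 11.1 plan baseline data, so this is a wording conflict and not an absence of data.

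**Total MME is a legitimate target.** Conditioning on visits changes the question, and the stated primary aim is feasibility. Both points stand. They argue against forcing a new primary outcome and for a lower severity. They do not remove the need to define the outcome and the handling of zero-visit weeks.

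**Nothing shows that volume changed.** Correct. The plan also offers no way to detect or adjust for it if it did.

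**Conclusion.** The point holds as an unresolved definition with a directional risk. It is certain from the text that the visit denominator is unused, that its window conflicts with the 34-week periods, and that zero-visit weeks have no stated handling. The bias is conditional. It requires that the outcome is a clinician-week total and that volume falls progressively or clinicians leave.

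Under the assumed inputs, a 20% ramp-down gave a false significant decline in 33% of runs, and 5 departures among 41 clinicians did so in 53%, against none with no change. These sizes depend on assumed visit counts, order rates, absence and the log(1 + MME) scale, with 40 runs each, so only the direction should be carried forward. Support for the log-visits adjustment comes from a fit without the clinician intercept and carries the same caution.

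Severity: should-fix, as this is a one-clinic feasibility pilot.

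**What to change.** 1. Section 4.1: apply the visit-eligibility rule to both 34-week periods and remove the conflict with the 6-month window.
2. Section 10: state whether the outcome is total MME per clinician-week or MME per eligible visit, and align sections 9.1 and 9.4.1 with it.
3. Section 10: treat clinician-weeks with no eligible visits as not observed, not as zero MME.
4. Section 10: fit the same model with log(eligible visits) added, at least as a prespecified sensitivity analysis beside total MME. Prefer this to a simple MME-per-visit ratio, which left part of the volume artefact.
5. Report eligible visits per clinician-week by period, so that any drift or departure can be seen.

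**Cost.** This needs protocol and SAP wording, and visit counts from records that sections 6.1 and 11.1 already plan to collect, provided the extract holds all eligible visits and not only those with an opioid order. Section 10 is partly in the past tense; if the analysis has been run, this is a re-analysis of data already held. The one statistical trade-off is that the visit-adjusted result is conditional on visits, so an effect that works through fewer visits would appear only in the total-MME result. That is why both should be reported.

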4.2 Exclusion Criteria

Visits will be excluded from the primary analysis when they have active cancer. Cancer exclusions (ICD-10 codes) are listed [here](#).

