6. STUDY PROCEDURES

6.1 Schedule of Evaluations

Assessment	Screening: Baseline prescribing	Baseline, Enrollment,	Intervention start (Month 1)	Continuously Measured or monitored	Intervention end: (Month 6)
Clinician-level Assessments					
Demographics	X				
Inclusion/Exclusion Criteria	X	X			
Visit-level assessments					
ICD-10 codes	X	X	X	X	X
Ordering Data	X	X	X	X	X
Adverse Events			X	X	X

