7.1 Specification of Safety Parameters

Data elements from qualifying visits for providers enrolled in the study will be collected from the electronic health record. Clinics will incorporate exclusions (ICD 10 cancer suppressor codes found [here](#)) used in the decision to trigger the clinical decision support. Aggregate counts of total visits across sites for which the intervention was triggered, for high dose opioid patients, if abrupt changes to dose ($> 20\%$ morphine equivalent daily dose) were made. Such cases will be examined closely to determine if unsafe drops in opioids occurred.

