11.3.3 Metrics

Quality control metrics will be based on reports verifying visits were not for cancer exclusions. All drugs prescribed at these visits will be categorized as “opioid” or “non-opioid”.

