APPENDIX A. OPIOID PRESCRIBING DIAGNOSES EXCLUSIONS AND MEDICATIONS FOR OUTCOMES ASSESSMENTS

Opioids Trigger List	Link	("Outcome" Tab)
Opioids Outcome List	Link	("Grouper" Tab)
Diagnosis of Exclusion	Link	
Non-Opioid Dosing for Alternatives	Link

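### The cancer exclusion may depend on codes recorded after go-live that also silence the alert, so a rise in cancer coding could look like a fall in prescribing

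*Combined protocol and SAP*

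**What the plan says.** Section 4.2 sets the outcome exclusion: "Visits will be excluded from the primary analysis when they have active cancer". It adds that "Cancer exclusions (ICD-10 codes) are listed" at a link, so the exclusion works from recorded codes. In the schedule in section 6.1, ICD-10 codes sit under "Visit-level assessments" and are collected at every time point, including after the intervention starts.

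Section 7.1 gives cancer codes a second function: "Clinics will incorporate exclusions (ICD 10 cancer suppressor codes found" at a link), and these are "used in the decision to trigger the clinical decision support". Appendix A has separate opioid lists for the trigger and for the outcome, but a single diagnosis list, "Diagnosis of Exclusion".

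Section 3 defines the endpoint: "The primary outcome is average weekly morphine milligram equivalents (MME) prescribed per-clinician". It compares 34 baseline weeks with 34 intervention weeks in 41 clinicians. Sections 6.2.2 and 9.2 confirm one clinic and no randomization. The section 10 model has time, time with a knot at intervention start and a clinician random intercept. It has no level-change term and no term for coding.

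Two quality checks touch on this. Section 11.3.3 says: "Quality control metrics will be based on reports verifying visits were not for cancer exclusions". Section 11.3.2 has practising clinicians review dashboards for deviations in coding and for appropriate code values. Neither section specifies a comparison of excluded visits or MME between periods, or any consequence for the analysis.

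**The concern.** At baseline, recording cancer at an opioid visit has no effect on the clinician's workflow. After go-live, a recorded cancer code can suppress a prompt that, for opioid-naïve and at-risk patients, asks for a written justification visible in the record (section 5.2). If the outcome exclusion reads codes entered at those visits, the analysis set is defined by a post-intervention variable that the intervention can influence. A visit newly coded for cancer takes its MME out of the intervention period, while a comparable baseline visit stays in. That works in the direction of the primary hypothesis.

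With no concurrent control, a shift in coding cannot be told apart from a shift in prescribing. Verifying that included visits carry no cancer code would not reveal it, because the visits that moved are no longer there. The pilot is also meant to lead to a cluster randomized trial, so the rule could carry forward.

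**Working it through.** The plan gives no cancer share, coding rate, effect size or sample-size figure, so there is nothing of its own to reproduce. The shares below are assumptions. True prescribing is held constant throughout.

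**1. Does the text link the two uses of the codes?** Section 4.2 removes visits by cancer code. Section 7.1 calls the exclusions suppressor codes and feeds them into the trigger. Appendix A splits the opioid lists by use but has one diagnosis list. A shared cancer list is therefore a strong inference, not a stated fact, because the links cannot be opened.

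**2. Before-after change in total counted MME.** Let c be the share of MME that goes to cancer patients and p the proportion of that MME carrying a cancer code. Counted MME is proportional to 1 − c·p, so

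change = (1 − c·p_post)/(1 − c·p_pre) − 1.

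| c | p before → after | Coded share of MME | Ratio | Change |
|---|---|---|---|---|
| 10% | 80% → 85% | 8.0% → 8.5% | 0.915/0.920 | −0.5% |
| 20% | 80% → 85% | 16% → 17% | 0.83/0.84 | −1.2% |
| 10% | 50% → 70% | 5% → 7% | 0.93/0.95 | −2.1% |
| 10% | 50% → 90% | 5% → 9% | 0.91/0.95 | −4.2% |
| 20% | 50% → 70% | 10% → 14% | 0.86/0.90 | −4.4% |
| 20% | 50% → 90% | 10% → 18% | 0.82/0.90 | −8.9% |

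If p does not change, the change is zero. If coding falls, the sign reverses. These ratios compare a coding level held throughout baseline with one held throughout the intervention period.

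**3. What the SAP's model would show.** I fitted log(1 − coded share) by least squares to the section 10 mean structure: intercept, time, and time after the knot, over 68 weeks with the knot at week 34. Censoring, the random intercept and noise were left out. Two shapes were tried for a coded share going from 5% to 10% (0.90/0.95 − 1 = −5.26% between the two levels).

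- *Gradual rise over the intervention weeks:* the knot term is −0.00164 per week. Over 34 weeks that is exp(−0.00164 × 34) − 1, about −5.4%. The common time slope is essentially zero, so the artefact falls almost entirely on the term that carries the intervention effect.
- *Abrupt step at go-live:* the knot term is +0.00007 per week, or +0.2% over 34 weeks. The model has no level term, so the step is spread as a common time slope of −0.00123 per week across both periods. The fitted decline over the intervention weeks is about 3.9%.

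The table in step 2 is therefore not an estimate of bias in the knot coefficient. How much reaches that coefficient depends on how quickly coding changes.

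**4. Zero weeks.** If opioid visits are Poisson with an assumed mean of 1.5 per clinician-week, and the 5% to 10% applies to visits, the share of zero-MME weeks goes from exp(−1.5 × 0.95) = 24% to exp(−1.5 × 0.90) = 26%. The number of censored weeks would also rise.

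**The case against.** The strongest reply is that the mechanism is only one possible implementation. Section 4.2 speaks of visits that have cancer, which can be read as patients who have cancer. Section 6.1 says at what level codes are collected, not that only the index visit's code counts. The documents do not say whether the exclusion or the suppressor reads encounter diagnoses or the problem list. If the suppressor reads cancer already on the problem list, a known cancer patient triggers no alert and there is nothing to gain by coding. This stands, and it is why the point is conditional.

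The incentive is also modest. A blank justification is accepted and simply recorded as such, and for long-term recipients section 5.2 describes only a prompt suggesting a taper. A reader might infer that cancer coding will become more complete after go-live, or that the analysis will show a spurious fall. The documents support neither: they contain no evidence on coding before or after go-live.

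A reader might also take 2% to 9% as the bias in the planned analysis. It is a ratio of totals under large assumed shifts. Smaller shifts give about 1% or less, and an abrupt step barely touches the knot term.

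Finally, the dashboards in section 11.3.2 might pick up a coding change. They are the nearest safeguard, but no period comparison is specified for them. What survives is that nothing in the plan fixes cancer status across periods or would quantify a shift.

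**Conclusion.** The vulnerability is real but conditional. It requires that the outcome exclusion reads codes recorded after go-live, that the suppressor uses the same or an overlapping list, and that coding changes. The documents make the first two plausible and say nothing on the third.

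The size is unknown: 0.5% to 8.9% for total counted MME under the assumptions shown, and zero if coding is stable. Whether it appears in the knot term or as a decline across both periods depends on the speed of the change.

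The direction is clear if the outcome is a weekly MME total. If it is a mean over opioid visits only, a reading that the outcome denominator in section 4.1 leaves open, it could reverse where newly excluded visits carry below-average MME.

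This does not invalidate a feasibility pilot. It is a worthwhile and inexpensive improvement, and goes beyond a request for missing detail because the remedy removes or reveals the bias.

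**What to change.** In sections 4.2 and 10, define the outcome exclusion by patient, with one status that applies to both periods. Two workable rules are:

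- any listed code dated before go-live, which alert-prompted coding cannot affect; or
- any listed code at any time in the study, with the patient removed from both periods.

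The first is stricter. Under the second, a patient whose only opioid orders fall at baseline has no opportunity for an alert-prompted code, so some asymmetry can remain. A rolling look-back that omits only the index visit would not be enough: a code prompted by the alert would still remove that patient's later intervention-period MME.

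State which record source is read (encounter diagnosis, problem list or both). Leave the alert suppressor as built. Report visits and MME excluded for cancer by period, and by week if possible, so that a step can be told from a gradual rise. Add two sensitivity analyses: the visit-level rule as now written, and no cancer exclusion.

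The cost is a wording change, one query on ICD-10 and ordering data already collected, and a small amount of extra analysis. The downside is some misclassification of patients whose cancer begins or resolves during the study. Under the pre-go-live rule, new cancers stay in the intervention period, which would tend to raise measured MME there.
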